6. GENERAL ANALYSIS DEFINITIONS

6.1 TREATMENTS

There will be three basic treatment phases in this trial: screening, study treatment phase (with either empagliflozin 10mg or matching placebo) and post-treatment. However, during the study treatment phase, patients are allowed to go off-treatment and subsequently re-start treatment. This may happen not at all or repeatedly for a given patient.

The purpose of the definitions below is to describe all the different study/treatment intervals, in which a patient can participate in during the course of the trial. Note that the term "treatment regimen" also covers the "off-treatment" time periods.

Table 6.1: 1 Treatment regimens / study intervals

Label	Interval	Start date
Screening	Screening	Date of informed consent
Placebo/ Empagliflozin 10mg	Treatment	Date of first administration of study medication
Off-treatment (if applicable)	During treatment interval, but not on treatment	Date of last administration of study medication before temporary discontinuation + 1 day
Placebo/ Empagliflozin 10mg (if applicable)	During treatment interval, after restart of study medication	Date study medication re-started
Post-treatment	Post-treatment	Date of last administration of study medication + 1 day

Details on the definition of the on-treatment period for different endpoints are listed in [Table 6.1:2](#). The efficacy analyses will follow the intention-to-treat (ITT) principle in assigning patients to treatment groups, i.e. patients will be analysed as randomised.

Safety analyses will also assign patients to the treatment group as randomised.

If a patient erroneously receives the wrong trial drug, all subsequent medication packs dispensed to the patient will still be for the treatment group to which the patient was randomised. Therefore, the adverse events will be analysed as per randomised treatment, which is expected to reflect the prevailing treatment.

In the exceptional case that a patient took the wrong treatment, adverse events may occur while being on the wrong treatment. Analyses of this data are described in [Section 7.8.1.6](#).

Table 6.1: 2 Endpoint specific assignment to the on-treatment phase

Endpoint	Last day of assignment to the on-treatment phase (days after last intake of study medication)
Adverse events	7
Safety laboratory measurements	3
Heart rate	1
Glycosylated haemoglobin (HbA _{1c})	7
Glucose	1
Body weight	1
Creatinine and estimated glomerular filtration rate (eGFR)	1
N-terminal pro B-type natriuretic peptide (NT-proBNP)	1
Blood pressure (BP)	1
Patient reported outcome	7

6.2 IMPORTANT PROTOCOL DEVIATIONS

A protocol deviation is important, if it affects the rights or safety of the patients or if it can potentially influence the primary outcome measure for the respective patients in a way that is neither negligible nor in accordance with the study objectives.

The important protocol deviations (iPDs) will be described in the clinical trial report (CTR). A listing of patients with medication code broken at the trial sites will be provided.

Table 6.2: 1 Important protocol deviations

Category / Code	Description		Requirements	Excluded from
A	Entrance criteria not met			
A1	Target indication not met			
	A1.07	Conditions on ejection fraction (EF) not met	Inclusion criterion #5 not met	None
	A1.08	Conditions on NT-proBNP not met	Inclusion criterion #8 not met	None
A2 /3	Eligibility criteria not met			

Table 6.2: 1 Important protocol deviations (cont.)

Category / Code	Description	Requirements	Excluded from
A2.04	eGFR out of range	Exclusion criterion #15 met	None
A3.51	Type 1 diabetes	Exclusion criterion #16 met	None
A3.55	Not currently hospitalised for the primary diagnosis of acute heart failure (de novo or decompensated chronic HF), regardless of EF	Inclusion criterion #4 not met	None
A3.56	Randomisation outside of window	Inclusion criterion #6 not met	None
A3.57	Patient not hemodynamically stabilised	Inclusion criterion #7 not met	None
A3.58	HF episode leading to hospitalisation not sufficiently treated	Inclusion criterion #9 not met	None
A3.60	Cardiogenic shock	Exclusion criterion #1 met	None
A3.61	Primary diagnosis is not acute heart failure	Exclusion criterion #2 met	None
A3.62	Primary diagnosis is acute heart failure not triggered by volume overload	Exclusion criterion #3 met	None
B	Informed consent		
B1	Informed consent not available	Informed consent date missing	All
B2	Informed consent too late	Informed consent date was after Visit 1	None
C	Trial medication and randomisation		
C1.02	Incorrect trial medication taken	Wrong medication taken for more than 20% of the overall treatment duration Can only be finally judged after data base lock (DBL), since unblinding information is required.	None
C3.01	Non-compliance with study drug intake	Compliance <80% or >120%	None
C4.01 ¹	Medication code broken inappropriately	Medication code was broken for no valid reason. Final decision at the DBL meeting based on medical judgement.	None
D	Concomitant medication		
D2.02	Use of prohibited medication	Review of eCRF for prohibited medication. Final decision at the DBL meeting based on medical judgement.	None
G	Study-specific analysis		
G3.50 ¹	Assessment order not followed that could influence PRO at baseline or Day 90	PRO measurements not before any other assessment at baseline or Day 90	None
I	Other safety-related deviations		
I2.01	Pregnancy		None

[figure not shown]
¹ needs to be checked at site by Local Clinical Monitors (CMLs) / Clinical Research Associates (CRAs) as these cannot be checked programmatically

6.3 SUBJECT SETS ANALYSED

The following patient sets are defined:

- **Screened Set (SCR)**
Consists of all patients screened for the trial, with informed consent given and who completed at least one screening procedure at Visit 1.
- **Randomised set (RS)**
This patient set includes all randomised patients, whether treated or not.
- **Treated set (TS)**
This patient set includes all patients who were dispensed study medication and were documented to have taken at least one dose of investigational treatment.

A Per Protocol Set (PPS) will not be specified for this trial.

6.5 POOLING OF CENTRES

This section is not applicable because centre/country is not included in the statistical model.

6.6 HANDLING OF MISSING DATA AND OUTLIERS

6.6.1 Imputation methods

There will be no imputation of data for safety analyses.

For patients who discontinue the trial treatment prematurely, all efforts will be made to follow patients for survival and for any other endpoints including the primary and secondary endpoints until the end of the trial.

Multiple imputations:

Missing data for the Kansas City Cardiomyopathy Questionnaire Total Symptom Score (KCCQ-TSS), as part of the stratified win ratio and NT-proBNP (log-transformed values) will be estimated using multiple imputation, according to whether patients are on-treatment or off-treatment.

Values measured after premature discontinuation of study drug will be included in the analyses. All available on- and off-treatment data up to the planned measurement at Day 90 will be included.

There will be different types of missing data to be considered for the imputation.

Table 6.6.1: 1 Adjusted multiple imputation “jump-to-placebo” approach – the missing data imputation method

Missing data imputation (Assumption of missingness)	Non-monotone	Monotone
On-treatment data	MCMC-MI ¹ (MAR ³)	SLR-MI ² (MAR)
Off-treatment ⁴ data	Jump-to-Placebo (MNAR ⁵)	Jump-to-Placebo (MNAR)

¹ Markov Chain Monte Carlo – Multiple imputation (MCMC-MI)

² Sequential linear regression – Multiple imputation (SLR-MI)

³ Missing at random (MAR)

⁴ Any instance of a patient discontinuing treatment will lead to all future measurements being considered as off-treatment.

⁵ Missing not at random (MNAR)

As the first step, the non-monotone on-treatment missing data will be imputed using Markov Chain Monte Carlo (MCMC) simulation and standard techniques; MI will be performed separately by treatment with baseline value as a continuous variable and HF status as a binary variable (de novo or decompensated chronic HF). One hundred imputations will be performed to ensure adequate efficiency and stability of the estimation for missing data. This step will be referred to as ‘MCMC-MI’.

For the monotone missing on-treatment data, a sequential linear regression MI approach will be used and referred to as ‘SLR-MI’. The MI will be performed on a data set only including on treatment data and once per imputation from the previous step. This procedure will impute values for all missing time points both on- and off-treatment, so imputations for off-treatment values will then be deleted. The regression models will be fitted separately by treatment and

include the baseline value as a continuous covariate, HF status as a class covariate and the values at previous time points as separate continuous covariates.

To impute the missing off-treatment data, a residual-based approach will be used to enact the 'jump-to-placebo'. Throughout this imputation, all observed off-treatment data will be temporarily removed and added back at the end. A covariate-adjusted difference between the relevant treatment arm and placebo (i.e. 0 for those in the placebo arm) will be calculated at each visit using ANCOVA (with HF status and treatment as categorical covariates and baseline value as a continuous covariate). Next, the relevant estimated treatment difference will be deducted from all observed data in the active treatment groups. Note that the adjustments are for the duration of the imputation only and the original values for the observed data will be in the final imputed data set.

SLR-MI will then be performed once per imputation upon this modified data but only including patients either with missing values and/or those in the placebo arm, ensuring imputations are performed using the placebo distribution. The models will include baseline value as a continuous covariate, HF status as a class covariate and the values at previous time points as separate continuous covariates. All missing data will therefore follow the distribution of the placebo arm, jumping from one arm's distribution to the placebo's at the point of missingness, while still accounting for past within-treatment performance (the residuals). After this imputation, all the original observed values (i.e. off-treatment values) will be restored.

For NT-proBNP, the AUC of change from baseline in log-transformed NT-proBNP level will be calculated using these imputed data sets (imputation performed on the log-transformed data first before AUC values are calculated). Then an ANCOVA model will be applied (see [Section 7.5.2](#)). Rubin's rules ([13](#)) will be used to combine treatment estimates across the 100 imputations. Missing values at Visits 2b and 2c will not be imputed, but observed values at these visits will be used.

For KCCQ-TSS, the stratified win ratio will be calculated using these imputed data sets, by combining with the non-imputed death and HFE data. Because the stratified win ratio is log-normally distributed ([10](#)), Rubin's rules ([13](#)) can be used on the log-transformed win ratios to combine treatment estimates across the 100 imputations.

The implicit assumption underlying the imputations and analyses is that unobserved off treatment patient measurements will lose any treatment effect immediately post-treatment discontinuation.

A more technical description of the method can be found in [Appendix 9.2](#).

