9.2 ALGORITHM FOR IMPUTATION ACCORDING TO JUMP-TO-PLACEBO METHOD

This algorithm imputes missing on-treatment data as MAR, and then imputes missing off-treatment data as MNAR by a jump-to-placebo method.

The conceptual approach is described by Carpenter et. al. (11). The implementation is planned as follows:

1. Remove any off-treatment data from dataset
2. Non-monotone missing data is imputed under MAR to create a monotone pattern
 - a. 100 imputations are performed by MCMC-MI, stratified by treatment, with the following parameters:
 - i. Baseline value included as a continuous variable, HF status as a binary variable (de novo or decompensated chronic HF)
 - ii. Multiple chains with 200 burn-in iterations per chain
 - iii. Jeffrey's prior
3. SLR-MI is used to impute missing monotone on-treatment data:
 - a. All data is imputed using SLR-MI, separately by treatment, with the following parameters:
 - i. Baseline (continuous), HF status (de novo or decompensated HF) included as covariates
 - ii. All imputed data for patients at an off-treatment time point is deleted
4. On-treatment group means are calculated for each imputation at each visit
 - a. ANCOVA used to calculate adjusted means with the following parameters:
 - i. Baseline (continuous), HF status (de novo or decompensated chronic HF), and treatment included as covariates
 - ii. Restricted Maximum Likelihood and Kenward-Rogers methods
 - iii. Least Square Means used
5. Placebo group on-treatment means at each visit are subtracted from all group on-treatment means at the same visit, to give treatment differences

- a. Note that these will be 0 for the placebo group
6. Individual data is ‘temporarily saved’ at this point, excluding available off-treatment data
7. Treatment differences are subtracted from the respective (by visit and treatment) data values
 - a. Results are the ‘residuals’ after removal of treatment effect(s)
 - b. This is referred to as the residual data
8. Subset of the residual data is created with all patients in placebo group and all patients with missing values at first visit requiring imputation. Note that these missing values will all be off-treatment.
9. Multiple imputation is performed on the first visit requiring imputation
 - a. Linear regression models are used to derive the distributional parameters;
 - i. One imputation per existing imputation
 - ii. Residual subset used

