 - iii. Baseline (continuous), HF status (de novo or decompensated chronic HF), all previous visits (continuous) included as model covariates
10. Imputed off-treatment values from subset merged with residual data sets.
11. If visits that require imputation remain, go to step 8, else proceed to next step
12. Original data set, saved data sets and residual data sets are merged so that all missing values in the saved data set are filled with observed off-treatment measurements where available, otherwise the values from corresponding residual data sets are used.
13. The next step depends on the data being imputed:
 - a. For NT-proBNP, the AUC of change from baseline in log-transformed NT-proBNP level will be calculated for these imputed data sets. Then an ANCOVA model will be applied (see [Section 7.5.2](#)).
 - b. For KCCQ-TSS, the stratified win ratio will be calculated using these imputed data sets, by combining with the non-imputed death and HFE data (see [Section 7.4.1](#)). Then take logs of the stratified win ratios.
14. Estimates and variances are combined using Rubin’s rules ([13](#)) to give a single estimate and variance for each parameter of interest across all imputations.

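### A missing Day 90 KCCQ-TSS is imputed without the patient's own observed off-treatment score from Day 15 or Day 30

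*SAP*

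**What the plan says.** SAP 6.6.1 and Appendix 9.2 describe the same procedure for KCCQ-TSS and log NT-proBNP.

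- Step 1 of Appendix 9.2: "Remove any off-treatment data from dataset". Section 6.6.1 confirms the timing: "Throughout this imputation, all observed off-treatment data will be temporarily removed and added back at the end".
- Steps 2 to 5 impute missing on-treatment values and estimate the on-treatment difference between arms at each visit. Step 7 subtracts that difference.
- Step 8: "Subset of the residual data is created with all patients in placebo group and all patients with missing values at first visit requiring imputation". Step 9 then imputes that visit by regression, with baseline, HF status and "all previous visits (continuous) included as model covariates". Steps 10 and 11 carry the imputed values forward and move to the next visit.
- Step 12: gaps are "filled with observed off-treatment measurements where available, otherwise the values from corresponding residual data sets are used".

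Section 6.6.1 says a patient's history enters "while still accounting for past within-treatment performance (the residuals"), that is, through on-treatment data. It gives the underlying assumption as "unobserved off treatment patient measurements will lose any treatment effect immediately post-treatment discontinuation". Footnote 4 of Table 6.6.1: 1 defines the off-treatment state broadly: "Any instance of a patient discontinuing treatment will lead to all future measurements being considered as off-treatment".

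The same section also says that on- and off-treatment data up to Day 90 will all be included, and SAP 7.4 describes the estimand as treatment-policy in style.

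**The concern.** Patients who stop drug are asked to keep attending to Day 90 (Protocol Flow Chart, footnote 3; Protocol 3.3.4.1), and KCCQ is scheduled at Days 15, 30 and 90. Some will give a score off drug at Day 15 or Day 30 and then have no Day 90 score. Protocol 3.3.4.1 allows for this: it accepts phone contact, or at least vital status and heart failure event information, when visits cannot be held.

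For these patients the most recent score is likely to be the best predictor of the missing one. The plan collects it, replaces it with a simulated value while Day 90 is imputed, and then restores it beside a Day 90 value that took no account of it. The primary endpoint uses only the Day 90 change, so restoring the earlier score has no effect on the win ratio. That fits poorly with the statement that all off-treatment data will be included.

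**Working it through.** **1. Trace one patient.** The patient stops after Day 15, has an off-treatment KCCQ-TSS at Day 30, and has no Day 90 score.

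| Step (SAP 9.2) | Day 30 | Day 90 |
|---|---|---|
| 1 | Observed score deleted | Missing |
| 8–10, first pass | Imputed from baseline, HF status, Day 15 | Missing |
| 8–10, second pass | Imputed value serves as predictor | Imputed from baseline, HF status, Day 15, imputed Day 30 |
| 12 | Observed score restored | Imputed value stays |

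No step re-imputes Day 90 after the restoration, so the observed Day 30 score has weight 0 in it.

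If Day 90 is observed off drug, step 12 restores it and it is used. Deaths and heart failure events are never imputed or removed. For NT-proBNP the outcome is the 30-day AUC, a secondary endpoint. A value is lost as a predictor there only when Day 30 is missing after an observed off-treatment Day 15, and that Day 15 value still enters the AUC once restored.

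**2. Size for one patient.** From Protocol 7.5: SD 20 and win threshold 5. Assumed, because the documents give no visit correlations: correlation ρ between 0.5 and 0.8, either equal between all visits or first-order autoregressive across the three visits. The weight that Day 30 would have in predicting Day 90, given Day 15, is:

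- equal correlation: ρ/(1+ρ), so 0.5/1.5 = 0.33, 0.7/1.7 = 0.41, 0.8/1.8 = 0.44
- autoregressive: ρ, so 0.5, 0.7, 0.8

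Shift in expected Day 90 = weight × (observed Day 30 minus the Day 30 value predicted from Day 15):

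- 10-point fall: from 0.33 × 10 = 3.3 to 0.80 × 10 = 8.0 points lower
- 20-point fall: from 6.7 to 16.0 points lower
- under the SAP: 0 in every case

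An improvement of the same size is ignored by the same amount in the other direction.

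**3. Size for the trial.** The plan states no figure for this. The stated power in Protocol 7.5 is 87.4%. Simulating that model gave 86.3% at an assumed frailty variance of 0.1 (the protocol does not state the variance) and 82.8% to 84.3% at variances of 0.5 to 4. That figure does not depend on the imputation and does not test this point.

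The KCCQ tier was simulated alone: 250 per arm, effect 6, SD 20, threshold 5, ρ = 0.7 under both correlation patterns, 600 runs per scenario. Affected patients had a persistent fall of 10 or 20 points off drug, an observed Day 30 and a missing Day 90. Their frequencies are assumed. Ranges run over the two patterns and two falls; the last column is the cell-by-cell difference.

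| Affected, empagliflozin vs placebo | True win ratio | SAP | Day 30 kept | SAP minus kept |
|---|---|---|---|---|
| 2% vs 2% | 1.453–1.467 | 1.456–1.473 | 1.456–1.468 | −0.001 to 0.005 |
| 5% vs 5% | 1.441–1.452 | 1.449–1.454 | 1.447–1.457 | −0.005 to 0.003 |
| 5% vs 2% | 1.389–1.431 | 1.440–1.456 | 1.410–1.438 | 0.011 to 0.039 |
| 10% vs 5% | 1.329–1.366 | 1.414–1.426 | 1.357–1.395 | 0.022 to 0.069 |

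In every unbalanced cell, keeping Day 30 lies between the SAP result and the truth. The simulation leaves out deaths, heart failure events and strata, treats the correlations as known, and uses one imputation per run.

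**The case against.** The procedure is deliberate, pre-specified and consistent between 6.6.1 and 9.2. Step 1 has a sound purpose: it keeps off-treatment data out of the on-treatment missing-at-random models and the on-treatment means in steps 2 to 5. That stands, and it limits the point to step 8 onward.

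The group is narrow. Day 90 must be missing and an earlier off-treatment score must exist. The protocol works to avoid this, including KCCQ completion at home under COVID-19 restrictions (Protocol 10.5). On-treatment visits remain predictors. Table 6.1: 2 counts patient-reported outcomes as on-treatment for 7 days after the last intake, so a score at an Early Discontinuation Visit may be kept, although the SAP does not say how that window combines with footnote 4. Worsening recorded as a heart failure event counts in a higher tier. All of this stands and bears on size.

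The stated assumption of immediate loss of effect concerns unobserved measurements. It does not show that every observed value classed as off-treatment is on the placebo scale. Restarting is allowed (Protocol 4.1.4; SAP 6.1), and under footnote 4 values taken back on empagliflozin still count as off-treatment. Putting those in unadjusted would carry drug effect into a placebo-based imputation. This is correct, and the fix has to treat them separately.

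Parts of the public SAP are missing after 7.4.1, so whether a sensitivity analysis already covers this cannot be judged.

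None of this removes the core point: a genuine measurement is replaced by a simulated one as a predictor, with no gain after step 7.

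**Conclusion.** The point holds in a limited form. When Day 90 KCCQ-TSS is missing after an observed off-treatment score at Day 15 or Day 30, the imputed value in tier 4 of the primary endpoint ignores that score. For a single patient the neglected shift can exceed the 5-point win threshold. For the trial the effect is probably very small if such patients are balanced between arms (0.005 or less on the KCCQ-tier win ratio) and larger only if they are more frequent, or worsen more, in one arm. These sizes rest on assumed correlations, frequencies and falls; the documents give none of them.

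A reader might infer that the primary result is biased towards empagliflozin, or that data collected after stopping drug are generally lost. The documents support neither. The rule ignores improvement as well as worsening, nothing in the documents shows an imbalance between arms, and off-treatment Day 90 scores, heart failure events and deaths are all used. For NT-proBNP the consequence is confined to a secondary endpoint evaluated in an exploratory manner.

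It is worth changing because it is cheap and brings the algorithm closer to the stated treatment-policy aim.

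**What to change.** Keep step 1 of Appendix 9.2 for the on-treatment models and means (steps 2 to 5). From step 8 onward, once a visit has been imputed, put each observed off-treatment value back at that visit before imputing the next, so that it serves as the previous-visit covariate in step 9. The regression is still fitted on placebo data.

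- Values taken truly off drug go in unadjusted.
- Values taken after restarting empagliflozin first have the same visit-specific treatment difference subtracted as in step 7. Step 12 still places the original observed value in the final data set.

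Amend the sentence in SAP 6.6.1 on temporary removal to match, and report by arm how many patients have an observed off-treatment Day 15 or Day 30 KCCQ-TSS with Day 90 missing.

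The cost is a slightly more complex imputation program, which must separate values taken off drug from those taken after a restart. No new data are needed.
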